3.4. Expectations and role to the project

The results and the associations revealed from the study will be used to feed NUTRISHIELD platform and train the personalized nutritional algorithm with data obtained from clinical settings, including from both pre- and full-term infants as well as infants fed both with OMM and DHM. This will in essence validate the NUTRISHIELD platform, describing how a theoretical framework designed and fed by the patients' data translates to clinical practice. What is more, evaluations performed in DHM before and after pasteurization/storage will provide input to the human milk analyzer that is developed within WP4, with focus on the determination of milk proteins that may change with thermal treatment of the milk.

3.6. Study CONSORT 2010 checklist

Table 3.1: Study II CONSORT 1

Section/Topic	Item No	Checklist item	Reported on page No
Title and abstract			10.
Title and abstract	1a	Identification as a randomised trial in the title	Non-applicable
	1b	Structured summary of trial design, methods, results, and conclusions (for specific guidance see CONSORT for abstracts)	Non-applicable
	10	Structured Suffilliary Of trial design, methods, results, and conclusions (for specific guidance see consok) for abstracts)	- Мон-аррисавіе
Introduction			
Background and	2a	Scientific background and explanation of rationale	28-29
objectives	2b	Specific objectives or hypotheses	28-29
Methods			
Trial design	3a	Description of trial design (such as parallel, factorial) including allocation ratio	29
-	3b	Important changes to methods after trial commencement (such as eligibility criteria), with reasons	Non-applicable
Participants	4a	Eligibility criteria for participants	31-32
·	4b	Settings and locations where the data were collected	31
Interventions	5	The interventions for each group with sufficient details to allow replication, including how and when they were actually administered	Non-applicable
Outcomes	6a	Completely defined pre-specified primary and secondary outcome measures, including how and when they were assessed	32-37
	6b	Any changes to trial outcomes after the trial commenced, with reasons	Non-applicable
Sample size	7a	How sample size was determined	37
•	7b	When applicable, explanation of any interim analyses and stopping guidelines	Non-applicable
Randomisation:			
Sequence	8a	Method used to generate the random allocation sequence	Non-applicable
generation	8b	Type of randomisation; details of any restriction (such as blocking and block size)	Non-applicable
Allocation	9	Mechanism used to implement the random allocation sequence (such as sequentially numbered containers),	Non-applicable
	-	,	

This document is part of a project that has received funding from the European Union's Horizon 2020 research and innovation programme under grant agreement No 818110. It is the property of the NUTRISHIELD consortium and shall not be distributed or reproduced without the formal approval of the NUTRISHIELD Management Committee. The content of this report reflects only the authors' view. EC is not responsible for any use that may be made of the information it contains.

concealment mechanism		describing any steps taken to conceal the sequence until interventions were assigned	
Implementation	Implementation 10 Who generated the random allocation sequence, who enrolled participants, and who assigned participants to interventions		Non-applicable
Blinding 11a		If done, who was blinded after assignment to interventions (for example, participants, care providers, those assessing outcomes) and how	
	11b	If relevant, description of the similarity of interventions	Non-applicable
Statistical methods	12a	Statistical methods used to compare groups for primary and secondary outcomes	37-38
	12b	Methods for additional analyses, such as subgroup analyses and adjusted analyses	Non-applicable
Results			
Participant flow (a diagram is strongly	13a	For each group, the numbers of participants who were randomly assigned, received intended treatment, and were analysed for the primary outcome	Non-applicable
recommended)	13b	For each group, losses and exclusions after randomisation, together with reasons	Non-applicable
Recruitment	14a	Dates defining the periods of recruitment and follow-up	Non-applicable
	14b	Why the trial ended or was stopped	Non-applicable
Baseline data	15	A table showing baseline demographic and clinical characteristics for each group	Non-applicable
Numbers analysed	16	For each group, number of participants (denominator) included in each analysis and whether the analysis was by original assigned groups	Non-applicable
Outcomes and estimation	17a	For each primary and secondary outcome, results for each group, and the estimated effect size and its precision (such as 95% confidence interval)	Non-applicable
	17b	For binary outcomes, presentation of both absolute and relative effect sizes is recommended	Non-applicable
Ancillary analyses	18	Results of any other analyses performed, including subgroup analyses and adjusted analyses, distinguishing pre-specified from exploratory	Non-applicable
Harms	19	All important harms or unintended effects in each group (for specific guidance see CONSORT for harms)	Non-applicable
Discussion			
Limitations	20	Trial limitations, addressing sources of potential bias, imprecision, and, if relevant, multiplicity of analyses	Non-applicable
Generalisability	21	Generalisability (external validity, applicability) of the trial findings	Non-applicable
Interpretation	22	Interpretation consistent with results, balancing benefits and harms, and considering other relevant evidence	Non-applicable
Other information			
Registration	23	Registration number and name of trial registry	Non-applicable

Draft, V1.2 – 28/06/2019 H2020 Contract No 818110

Protocol	24	Where the full trial protocol can be accessed, if available	Non-applicable
Funding	25	Sources of funding and other support (such as supply of drugs), role of funders	Non-applicable

Project Acronym: Nutrishield

Grant Agreement number: 818110 (H2020-SFS-2018-IA)

Project Full Title: Fact-based personalised nutrition for the young

4. Study III protocol: Personalised nutrition against cognitive decline for children

4.1. Background

A diet of sufficient quantity and quality is crucial for children's growth and mental development. An excess in energy intake, along with reduced energy expenditure, has contributed to the modern epidemic of pediatric obesity [1], while in the same time estimates of undernutrition remain concerning [1]. This double burden of malnutrition poses great risk for children's current and future health and well being [2-5].

Beyond nutrient and energy intake per se, literature suggests that dietary quality has a major imprint on children's health as well. Lower dietary quality in children has been previously associated with worse sleep indices [6], higher prevalence of excess weight and central adiposity [7-12], breathing anomalies [13], and poor cardiometabolic health [14-16]. Furthermore, evidence suggests that higher adherence to a variety of healthful dietary patterns is associated with enhanced neurocognitive development [17], reportedly more profound in boys [18]. Last, better diet quality has been associated with improved academic performance [19].

Evidence is accumulating concerning the effects of dietary intake and quality of children in other health outcomes. For instance, the interrelationship between the diet and gut microbiota and its impact on children's health has been a potent area of interest in recent years. Diet has been described as a main driver of the composition and function of gut microbiota [20]; however, their relationship has been mostly studied in very specific pediatric populations (i.e. children with epilepsy, autism, gastrointestinal diseases) [21-23]. Some results from healthy children have indicated that children with worse diet quality have reduced colonic short chain fatty acid fermentation compared to children with better diet quality [24]. Similar results have been produced in children adhering to a Western dietary pattern, compared to a traditional one [25, 26]. Nevertheless, conclusions are yet to be drawn on how these findings affect pediatric development. In addition, cross-matching of dietary indices with other individual measures, such as breath markers, may also highlight potential targets for optimal growth.

4.2. Objectives

The objective of this study is:

a) to evaluate the association of diet with health-related parameters, i.e. how the quality of the diet affects health related parameters (i.e. gut microbiota, breath analyses)

4.3. Methods

Overall study design, participants, measurements, sampling and statistical analysis are described in the following sections.

4.3.1. Study design

The proposed study is an observational trial, part of a trial in progress, performed by Stichting Kathoelike Universtiteit, in collaboration with Donders Institute, the Netherlands. It is entitled "Neural development of spatial cognition: an fMRI study on the effects of current and past nutritional status" (Principal Investigator: [name], Donders Institute). The trial is aiming to examine the relationship of nutritional status with the neural development of spatial cognition in 8-10 year old children. The part of the trial under NUTRISHIELD will be observational, and takes place at its baseline. During recruitment (observational phase) participants will be assessed once, as described below.

The trial is funded by the European Regional Development Fund (ERDF, PROJ-00405). Ethical approval for the ERDF trial has been granted by the Medical Ethical Committee of Radboud University Medical Center (date of approval: 22/05/2018; registration number: 2017-3923; NL-number: NL64464.091.17). Written informed consent will be obtained prior to participation. All procedures regarding data security and handling in the context of NUTRISHIELD will be in absolute accordance with the principles set under WP 9, concerning Ethical Requirements, and more specifically stated on Tasks 7.1 and 7.2 and D 7.2.

[figure not shown]
H2020 Contract No 818110

4.3.1.1. Schematic study design

The design and the measures acquired at the baseline of the ERDF trial along with the role of NUTRISHIELD are presented schematically in Figure 4.1 below.

Figure 4.1: Role of NUTRISHIELD 1 within ERDF trial

The part of the joined action between NUTRISHIELD and ERDF highlighted in green.

4.3.2. Participants

The study sample will include 55 healthy children, aged 8-10 years old.

4.3.3. Baseline Study Phase

4.3.3.1. Measurements

Under the ERDF study protocol, all participants will be evaluated, including dietary intake, nutritional status, body composition, inflammatory markers and epigenetics, afterwards explored as intermediates in the relationship between the children's diet and spatial cognition. In collaboration with NUTRISHIELD, analyses of breath, and gut microbiome will be carried out in the study population.

o Sociodemographic information

ERDF trial.

Dietary assessment

45-minute Food Frequency Questionnaire (ERDF trial).

Anthropometric assessment

Weight, height, computation of BMI, measures of abdominal fat by Magnetic Resonance Tomography (ERDF trial).

Inflammatory assessment

Measured in children's saliva (ERDF trial).Inflammatory assessment is funded by an external company. Thus, using these measures under NUTRISHIELD warrants the company's approval.

o Genotype characterisation

Buccal swaps, DNA methylation patterns (ERDF trial). Epigenetics assessment is funded by an external company. Thus, using these measures under NUTRISHIELD warrants the company's approval.

Microbiome assessment

[figure not shown]
Fecal samples from children will be collected for studying the microbiome at baseline. The protocol followed is described in Deliverable 2.1.

Breath analyses

Breath measures of children will be collected, and novel markers will be analyzed. The protocol followed is described in Deliverable 2.4.

4.3.4. Sample size

A sample size of 55 children, aged 8-10, has been found adequate to significantly detect expected outcomes of the ERDF trial.

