BMI	Body Mass Index
CEN	Complete Enteral Nutrition
CONSORT	Consolidated Standards for Reporting Clinical Trials
DHM	Donor Human Milk
ERDF	European Regional Development Fund
FFQ	Food Frequency Questionnaire
FT-OMM	Full term infants receiving OMM
HM	Human Milk
HULAFE	University and Polytechnic Hospital La Fe
IPAQ	International Physical Activity Questionnaire
KIDMED	Mediterranean Diet Quality Index
MedDietScore	Mediterranean Diet Score
OMM	Own Mother's Milk
PT-DHM	Pre-term infants fed with pasteurized DHM
PT-OMM	Pre-term infants fed with OMM
RBW	Recover of birth weight
T2DM	Type 2 Diabetes Mellitus
WP	Work Package
YAP	Youth Activity Profile

H2020 Contract No 818110

1. Preamble

The NUTRISHIELD platform will be validated through three clinical studies, where the efficacy of the NUTRISHIELD technology and methodology will be tested and validated. Three clinical studies, namely Study I, Study II and Study III, will be implemented in parts (Study III), or totally (Studies I and II) within NUTRISHIELD, each one aiming to produce input regarding different aspects of the NUTRISHIELD project. To this direction, different health conditions, population and settings will be used.

- Study I Obesity/Diabetes, will validate the nutrition algorithm developed based on personalised data of children having obesity and/or diabetes, through an observational and an intervention protocol.
- Study II Human milk, the results obtained from this observational study will be used to feed and then train the NUTRISHIELD personalized algorithm with data obtained from clinical settings, including both pre- and full-term infants, to be used as an asset for future reference.
- Study III- Cognitive decline, important associations of nutritional (abdominal fat measures) and other health-related parameters (epigenetics, inflammatory markers) will be revealed.

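### Study III calls every association at p 0.05 significant across an open marker screen, in a sample of 55 inherited from its parent trial and not sized for those associations

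*Protocol*

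**What the plan says.** Section 4.3.1 places Study III inside the ERDF trial: "The part of the trial under NUTRISHIELD will be observational, and takes place at its baseline". Of the ERDF trial it says: "The trial is aiming to examine the relationship of nutritional status with the neural development of spatial cognition in 8-10 year old children".

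The only objective in section 4.2 is the association of diet with health-related parameters, spelled out as "how the quality of the diet affects health related parameters (i.e. gut microbiota, breath analyses". Section 4.3.3.1 confirms that these two measures are what the project adds: "In collaboration with NUTRISHIELD, analyses of breath, and gut microbiome will be carried out in the study population".

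On size, section 4.3.2 states: "The study sample will include 55 healthy children, aged 8-10 years old". Section 4.3.4 is a single sentence, saying that this number "has been found adequate to significantly detect expected outcomes of the ERDF trial". It gives no effect size, variance, power or test.

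Section 4.3.5 plans to explore acquired measures against diet, and acquired measures other than diet against each other. It uses chi-square tests, t-tests and Spearman correlations, and sets 0.05 as the significance level without qualification.

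The Preamble describes Study III differently from section 4.2: "important associations of nutritional (abdominal fat measures) and other health-related parameters (epigenetics, inflammatory markers) will be revealed". Section 4.3.3.1 says of both the inflammatory and the epigenetic data: "Thus, using these measures under NUTRISHIELD warrants" the approval of the outside company that funds them.

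**The concern.** The sample-size section answers a question that Study III does not ask. Whatever 55 was found adequate for in the ERDF trial, the protocol nowhere relates it to microbiota or breath markers, so a reader cannot tell what size of association the add-on could detect.

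The significance rule makes this matter more. Microbiome and breath analyses usually yield many variables, and section 4.3.5 covers marker-to-marker as well as diet-to-marker associations. A flat 0.05 label across such a screen will produce chance findings called significant. The summary at the front of the protocol says the studies' findings will feed the platform, so that label has a use beyond a descriptive report.

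**Working it through.** **Can the stated number be reproduced?** No. Section 4.3.4 gives 55 and a reference to the ERDF outcomes, with nothing to calculate from. What can be calculated is what 55 children detect.

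**Inputs**
- n = 55 (sections 4.3.2 and 4.3.4).
- Significance level 0.05 (section 4.3.5). Sidedness is not stated; two-sided is assumed.
- Spearman correlation for continuous variables (section 4.3.5).
- All 55 children are assumed to have usable data.

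**Single test.** Fisher z approximation with the usual Spearman variance:

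standard error = √(1.06/(n − 3)) = √(1.06/52) = 0.1428

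smallest detectable r = tanh[(z for alpha + z for power) × standard error]

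- 80% power: tanh[(1.960 + 0.842) × 0.1428] = tanh(0.400) = 0.38
- 90% power: tanh[(1.960 + 1.282) × 0.1428] = tanh(0.463) = 0.43

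Power at a given r is Φ(atanh(r)/0.1428 − 1.960):

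| r | power |
|---|---|
| 0.20 | 29% |
| 0.30 | 58% |
| 0.33 | 67% |
| 0.40 | 84% |

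The row r = 0.33 is the correlation named for Study I phase I in section 2.3.5.1. It is borrowed as a yardstick only; the protocol sets no target for Study III.

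**Many tests at 0.05.** The protocol gives no number of markers, so a range is assumed. For m independent tests with no true association, the expected number of false positives is 0.05m and the chance of at least one is 1 − 0.95^m. The last column is the correlation needed for 80% power if alpha is split as 0.05/m.

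| m (assumed) | expected false positives | chance of at least one | r for 80% power at 0.05/m |
|---|---|---|---|
| 10 | 0.5 | 40% | 0.48 |
| 20 | 1 | 64% | 0.50 |
| 50 | 2.5 | 92% | 0.53 |
| 100 | 5 | 99% | 0.55 |

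A false-discovery-rate procedure at 0.05 uses per-marker thresholds between 0.05/m and 0.05. Its detectable correlation therefore lies between 0.38 and the last column, nearer 0.38 when many associations are real.

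**The outcome descriptions side by side.** The Preamble names abdominal fat, epigenetics and inflammation. Section 4.2 names microbiota and breath. Section 4.4 joins them: ERDF measures are to be related to those studied under the project. Section 4.3.5 provides for both kinds of link. The Preamble thus gives one half of the planned association and section 4.2 the other.

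**The case against.** The strongest reply is that Study III is exploratory and claims nothing confirmatory. Section 4.3.5 speaks of exploring associations, the checklist in section 4.6 marks prespecified outcomes as not applicable, and section 4.3.4 says openly that adequacy refers to the ERDF trial. Error control in a marker screen is often left to a statistical analysis plan, and section 4.3.5 defers additional analysis to deliverable D2.5.

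Much of this stands. The sentence in section 4.3.4 is uninformative for Study III, but it is not false. The absence of a multiplicity plan alone would not be a finding. What remains is that section 4.3.5 does state a rule, an unqualified 0.05 for significance, and that rule suits an open screen poorly.

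Four stronger readings are tempting, and the protocol does not support them:
- *That the sample size comes from an unrelated trial.* Study III is nested in the ERDF trial and uses its children. The outcomes differ, not the sample.
- *That 55 was found adequate for none of the measures named.* Section 4.3.3.1 lists body composition, inflammatory markers and epigenetics as ERDF measures, explored as intermediates between diet and spatial cognition. They may be among the ERDF trial's expected outcomes, which are not listed. The gap is shown only for microbiota and breath.
- *That the Preamble and section 4.2 set rival outcome lists.* Section 4.4 shows them to be two sides of one planned association.
- *That 55 is too small.* No target effect is given, and 55 gives more than 80% power for a single correlation of 0.40.

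**Conclusion.** The point holds in limited form. Section 4.3.4 gives no basis for judging what 55 children can show about diet with microbiota or breath, and section 4.3.5 applies a flat 0.05 to an open set of associations whose results are to be used downstream.

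The limit for a single test is |r| of about 0.38 at 80% power, given two-sided testing, complete data and the Fisher z approximation. The multiplicity figures depend on an assumed number of independent markers; 100 is an illustration, not a count from the protocol.

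The significance rule is the part that would change results. The sample-size sentence and the descriptions of scope are matters of wording. The Preamble's promise is the least supported wording, because two of the three measures it names depend on an outside approval that it does not mention.

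**What to change.** 1. **Section 4.3.5.** Replace the unqualified 0.05 rule with false-discovery-rate control across the microbiome and breath marker screen, and label unadjusted p-values as exploratory. The cost is one standard analysis step and lower power per marker.

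2. **Section 4.3.4.** State that 55 is fixed by the parent trial and was not chosen for Study III's associations. Add that a single two-sided 5% Spearman test in 55 children has 80% power for |r| of about 0.38 and 58% power at r = 0.30, before any multiplicity adjustment. Do not attach this to a prespecified association, because Study III has none.

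3. **Preamble and section 4.2 (minor).** Align both with section 4.4, so that each describes ERDF measures being related to the project's measures. Make use of the epigenetic and inflammatory data conditional on the company approval noted in section 4.3.3.1.

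Items 2 and 3 cost only wording, although the stated adequacy will read less favourably. No item needs more children or new measurements.

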4.3.5. Statistical analysis

Association of acquired measures with dietary measures will be explored. Additionally, the relationship in between acquired measures, other than dietary intake, will be studied. Categorical values will be explored with Chi-square analysis. Student's t-test will be employed to test associations of continuous, independent variables. Correlations between continuous variables will be tested with Spearman's r coefficient. A p-value of 0.05 is considered significant.

Statistical analyses will be performed with the use of STATA statistical software (STATA Corp LLL, College Station, TX, USA).

Finally, additional statistical analysis with the view of deriving additional insights and influences in personalised nutrition will be presented in D2.5.

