Implementation	10	Who generated the random allocation sequence, who enrolled participants, and who assigned	Non-
		participants to interventions	applicable
Blinding	11a	If done, who was blinded after assignment to interventions (for example, participants, care providers,	Non-
		those assessing outcomes) and how	applicable
	11b	If relevant, description of the similarity of interventions	Non-
			applicable
Statistical methods	12a	Statistical methods used to compare groups for primary and secondary outcomes	48
	12b	Methods for additional analyses, such as subgroup analyses and adjusted analyses	48
Results			
Participant flow (a	13a	For each group, the numbers of participants who were randomly assigned, received intended	Non-
diagram is strongly		treatment, and were analysed for the primary outcome	applicable
ecommended)	13b	For each group, losses and exclusions after randomisation, together with reasons	Non-
•			applicable
Recruitment	14a	Dates defining the periods of recruitment and follow-up	Non-
			applicable
	14b	Why the trial ended or was stopped	Non-
			Page 52

Draft, V1.2 – 28/06/2019 H2020 Contract No 818110

			applicable
Baseline data	15	A table showing baseline demographic and clinical characteristics for each group	Non-
			applicable
Numbers analysed	16	For each group, number of participants (denominator) included in each analysis and whether the	Non-
		analysis was by original assigned groups	applicable
Outcomes and	17a	For each primary and secondary outcome, results for each group, and the estimated effect size and its	Non-
estimation		precision (such as 95% confidence interval)	applicable
	17b	For binary outcomes, presentation of both absolute and relative effect sizes is recommended	Non-
			applicable
Ancillary analyses	18	Results of any other analyses performed, including subgroup analyses and adjusted analyses,	Non-
		distinguishing pre-specified from exploratory	applicable
Harms	19	All important harms or unintended effects in each group (for specific guidance see CONSORT for harms)	Non-
			applicable
Discussion			
Limitations	20	Trial limitations, addressing sources of potential bias, imprecision, and, if relevant, multiplicity of	Non-
		analyses	applicable
Generalisability	21	Generalisability (external validity, applicability) of the trial findings	Non-
			applicable
Interpretation	22	Interpretation consistent with results, balancing benefits and harms, and considering other relevant	Non-
		evidence	applicable
Other information			

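### Study III names only unadjusted bivariate tests for its diet–marker associations, so confounding can appear as a diet association

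*Protocol*

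**What the plan says.** Section 4.3.1 describes Study III as one part of a host trial that is already running: "The part of the trial under NUTRISHIELD will be observational, and takes place at its baseline". Children are assessed once and diet is not allocated. Section 4.3.4 takes the sample size from the host trial: "A sample size of 55 children, aged 8-10, has been found adequate to significantly detect expected outcomes of the ERDF trial".

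The single objective in section 4.2 opens with the association of diet with health-related parameters. It then explains this as "how the quality of the diet affects health related parameters", naming gut microbiota and breath analyses.

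Section 4.3.5 sets a significance level of 0.05 and names three methods. "Categorical values will be explored with Chi-square analysis"; Student's t-test is for continuous variables; and "Correlations between continuous variables will be tested with Spearman's r coefficient". It gives no covariate, regression model, partial correlation or stratification. Its last sentence sends further, unspecified analysis to deliverable D2.5.

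In the Study III checklist (section 4.6), item 12b, "Methods for additional analyses, such as subgroup analyses and adjusted analyses", is marked as reported on page 48. The table of contents places section 4.3.5 on that page.

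Section 4.3.3.1 lists sociodemographic information, weight, height, BMI and abdominal fat as host-trial data.

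**The concern.** In a cross-sectional sample without allocation of diet, children who eat better also differ in other ways. Family education or income, sex, and age within the 8–10 band can each be related to diet quality and to a microbiome or breath marker. A bivariate test cannot separate such a factor from diet. Section 4.4 links the study to evidence-based personalised nutrition, so a marker that follows family background could enter that work as a diet signal.

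This goes beyond detail that a protocol may leave to a later analysis plan. The protocol has chosen the tests, and its checklist says that additional methods, with adjusted analyses as an example, are reported at that place. The other two studies in the document do provide for adjustment. Study II (section 3.3.6) names prematurity, age and years of education as covariates, and Study I (section 2.3.6) promises necessary adjustments.

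**Working it through.** **What there is to reproduce.** The plan gives no effect size, power or endpoint behind the 55, so that figure cannot be recalculated. The point concerns the method; the arithmetic below only gives its scale.

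**Inputs.** n = 55 (section 4.3.4). α = 0.05 (section 4.3.5), taken as two-sided because sidedness is not stated. Confounder strength *b* is an assumption; the documents give none.

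**Model.** There is one confounder C and no direct link between diet D and marker M:

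D = b·C + √(1 − b²)·e₁ and M = b·C + √(1 − b²)·e₂, so the induced correlation is b × b = b².

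**Planned test.** Spearman's r, with t = r·√[(n − 2)/(1 − r²)] on 53 degrees of freedom. It is significant beyond about |r| = 0.27.

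**Adjusted test.** Partial Spearman, r(DM·C) = (r_DM − r_DC·r_MC) / √[(1 − r_DC²)(1 − r_MC²)], with t on 52 degrees of freedom.

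Share of simulated samples (20,000 per setting) significant at 5%, with no diet effect:

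| Assumed b | Induced r = b² | Unadjusted Spearman | Partial Spearman, C measured without error |
|---|---|---|---|
| 0.1 | 0.01 | about 5% | about 5% |
| 0.2 | 0.04 | about 6% | about 5% |
| 0.3 | 0.09 | 9 to 10% | about 5% |
| 0.4 | 0.16 | about 20% | about 5% |
| 0.5 | 0.25 | 41 to 42% | about 5% |

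**Limit of adjustment.** If the recorded confounder has a reliability of only 0.4 to 0.6 (also an assumption), the partial test still rejects in about 8 to 11% of samples at b = 0.4 and about 14 to 22% at b = 0.5.

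**Cost of adjustment.** The standard error of Fisher's z with k covariates is 1/√(n − 3 − k), so relative to no covariates it grows by √[52/(52 − k)].

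- k = 3 (age, sex, one socioeconomic measure): √(52/49) = 1.03.
- k = 4 (BMI added): √(52/48) = 1.04.

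The correlation detectable with 80% power is tanh[(1.960 + 0.842)/√(52 − k)]. This gives 0.370 with no covariates, 0.380 with three and 0.384 with four. Power at r = 0.37 falls from 80% to 78% and 77% respectively.

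**The checklist against the text.** Item 12b is marked non-applicable for Studies I and II but given a page for Study III. On that page, the only sentence that could answer it is the deferral to D2.5, which names no method.

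**The case against.** The strongest reply is that Study III is a small exploratory addition to another trial and mostly describes itself that way. The objective opens with association, section 4.3.5 says that associations will be explored, and D2.5 may contain more. This stands in part and limits what can be said. Four stronger readings are tempting, and the documents do not support them.

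- *That no adjusted analysis will ever be done.* D2.5 is not available. Nothing says that it adjusts for confounding, and nothing says that it does not. The gap is in what section 4.3.5 fixes.
- *That confounders will be reported as diet effects.* They can be. No confounder strength is given, and at 0.1 to 0.2 the problem nearly vanishes. The children are healthy and aged 8–10, which limits confounding by illness and age.
- *That the collected body measures are never used.* Section 4.3.5 also plans to relate non-dietary measures to each other, which covers BMI and abdominal fat. They are not assigned as covariates, which is a narrower statement.
- *That item 12b is plainly false.* Its wording gives adjusted analyses as an example, and the page does mention additional analysis. The pointer is empty of method rather than provably wrong.

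Two cautions apply to the remedy. Section 4.3.3.1 does not say which sociodemographic items the host trial holds; parental education and income appear in the general dictionary (Appendix 5.1), not in a list specific to Study III. BMI may lie between diet and marker: section 4.3.3.1 treats body composition as an intermediate, there between diet and spatial cognition.

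**Conclusion.** The point holds in a limited form. For an observational, once-assessed sample of 55, section 4.3.5 specifies only unadjusted tests, although the objective is partly worded as an effect and the checklist points there for adjusted analyses. Results produced as written are open to confounding.

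With one shared confounder and no diet effect, the false-positive rate ranges from essentially nominal at strengths of 0.1 to 0.2 to about two in five at 0.5. These figures rest on assumed strengths, equal for diet and marker, and on normally distributed variables. Adjustment restores the nominal rate only for confounders that are recorded and well measured; it reduces the problem without removing it. Because adjustment costs little precision and Study II already works this way, the change is worth making.

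**What to change.** 1. In section 4.3.5, make the main diet–marker analysis a partial Spearman correlation, or a linear regression on ranks, adjusted for age, sex and one socioeconomic measure (parental education or income). First confirm that the host trial holds that measure and will share it.
2. Add BMI only in a second model, labelled as such because it may be a mediator.
3. Keep the chi-square, t-test and bivariate Spearman results as description.
4. In section 4.2, replace *affects* with *is associated with*.
5. Correct item 12b in section 4.6 so that it points to the adjusted analysis, or mark it non-applicable if none is added.

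The cost is wording, access to host-trial variables, and three or four degrees of freedom (standard error up about 3 to 4%). No new measurement is needed if the socioeconomic item is confirmed. If it is not available, the protocol should say that the associations are not adjusted for family background.
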